8.3.3 Maintenance dosage and dosage adjustments

(1) MT-6548 Tablet

Maintenance dosage is 150–600 mg once daily and adjusted according to the dosage

adjustment guideline below.

(2) Darbepoetin alfa injection

The maintenance dosage is 5–180 µg per dose once a week, once every 2 weeks, or once every 4 weeks, which will be adjusted as appropriate according to the dosage adjustment guidelines below.

[Dosage adjustment guidelines]

Investigators/subinvestigators will monitor Hb levels throughout the treatment period, and determine whether to adjust study drug dosage or discontinue administration as required. In principle, dosage adjustment will be performed at scheduled visits or on the day of darbepoetin alfa injection; however, an additional visit may be provided for dosage adjustment, if considered necessary, in cases where excessive increases or decreases in Hb levels are of concern based on the Hb time course. In principle, dosage of MT-6548 Tablets and darbepoetin alfa injection will be adjusted simultaneously. If interruption of study drug administration is necessary, administration of MT-6548 Tablets and darbepoetin alfa injection should be discontinued, and if study drug administration is resumed, administration of both drugs should be resumed.

Hb levels will be measured in samples collected in the supine position using a HemoCue® Hb201 DM analyzer; and in principle, these measurements will be used to determine dosage adjustments. Hb levels on the day of dialysis will be measured in samples collected before dialysis. Hb measurements used for dosage adjustment determinations will be recorded in the subject's CRF. Measurement results from the HemoCue® Hb201 DM will be used solely for determination of study drug dosage adjustments, and will not be used for efficacy or safety analysis.

The dosage adjustment algorithm below will be followed in order to maintain Hb levels of 10.0–12.0 g/dL during the study. Dosage steps are defined in the dosage adjustment table below.

MT-6548 Tablet dosage adjustment table

Step	No. of tablets	Dosage
1	1	150 mg or placebo
2	2	300 mg or placebo
3	3	450 mg or placebo
4	4	600 mg or placebo

Darbepoetin alfa injection dosage adjustment table

Step	Dosage
1	5 µg or placebo
2	10 µg or placebo
3	15 µg or placebo
4	20 µg or placebo
5	30 µg or placebo
6	40 µg or placebo
7	50 µg or placebo
8	60 µg or placebo
9	80 µg or placebo
10	100 µg or placebo
11	120 µg or placebo
12	140 µg or placebo
13	160 µg or placebo

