14	180 µg or placebo

*It is permitted for dosage adjustments not to comply with the dosage adjustment algorithm for safety reasons depending on factors such as clinical status (e.g., AEs, volume depletion, or volume overload), Hb elevation rate, decrease rate, or fluctuations. In such cases, clinical status will be recorded in CRFs. All dosage increases of MT-6548 will be in increments of 1 tablet at a time.

If a dosage increase or reduction according to the dosage adjustment algorithm is impossible because the maximum or minimum dosage on the dosage adjustment table is already being administered, it is permitted to not alter the dosage at that point. However, in this case it will be confirmed whether withdrawal criteria are met, and treatment discontinued if so.

Dosage adjustment algorithm

- ✓ Dosage increases of MT-6548 Tablets should be performed at intervals of at least 4 weeks in principle, and dosage decreases at intervals of at least 2 weeks. Dosage increases and decreases of darbepoetin alfa injection should be performed at intervals of 2 weeks in principle.
- ✓ If Hb levels suddenly increase (>2.0 g/dL change in the past 4 weeks*), the dose should be decreased by 1 step.
- ✓ The dose should be increased by 1 step if Hb levels are <10.0 g/dL. However, decrease by

1 step instead of increasing in cases of sudden increase in Hb (more than 2.0 g/dL change in past 4 weeks*).

- ✓ The dose should be decreased by 1 step if Hb levels are >11.5 g/dL.
- ✓ If Hb levels are >12.0 g/dL and ≤ 13.0 g/dL with a rapid increase in Hb levels (>2.0 g/dL change in the past 4 weeks*), study drug administration should be discontinued, and the dose should be decreased by 1 step and administration resumed after Hb levels decrease to ≤ 12.0 g/dL.
- ✓ If Hb levels are >13.0 g/dL, study drug administration should be discontinued, and the dose should be decreased by 1 step and administration resumed after Hb levels decrease to ≤ 12.0 g/dL.
- ✓ (Criteria only for darbepoetin alfa injection) If Hb levels are maintained in the range of 10.0–11.5 g/dL, the dose may be twice the single dose at that time, and the dose interval changed from once every week to once every 2 weeks, or from once every 2 weeks to once every 4 weeks.

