### 4.6 Number of days of drug interruptions

The number of days of drug interruptions does not include subject's forgetting to take the drug and is defined by the following formula.

Number of days of drug interruptions (days) = Day of resumption of study drug administration – First day of study drug interruption

If there are multiple interruptions, the sum of them should be used.

Resumption date of study drug administration: After the entry of "Daily Dose" = 0 mg or 0 µg in the CRF, the first dose should be taken when a value of >0 mg is entered for the first time or should be administered when a value of >0 µg is entered for the first time. If the drug interruption continues until Week 52 of the treatment period, days should be calculated based on the visit date after Week 52 of the treatment period as the resumption date. Specifically, if the treatment is completed or discontinued while the drug is interrupted, the day before the day of blood sampling at Week 52 for hematology tests or the day before the day of treatment discontinuation should be used.

First day of study drug interruption: The day of administration when "Daily Dose" = 0 mg or 0 µg is first entered in the CRF.

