## 4.10 Mean daily dose/mean weekly dose

Mean daily dose of MT-6548 during each scheduled study visit period\* = Daily dose based on the physician's prescription  $\times$  Period of administration (days)\*3 of the corresponding dose\*2 between the scheduled study visits\*/Period between the scheduled study visits (days)\*4

Mean weekly dose of darbepoetin alfa during each scheduled study visit period\* = Daily dose based on the physician's prescription  $\times$  Period of administration (days)\*5 of the corresponding dose\*2 between the scheduled study visits\*/Period between the scheduled study visits (days)\*4  $\times$  7

\*: For each period between the scheduled study visits, the actual study visit dates will not be considered, and this variable should be fixed as follows:

- ✓ The first day of the treatment period to Week 2 of the treatment period: The first day of the treatment period (Day 1) to 14 days

- ✓ Week 2 of the treatment period to Week 4 of the treatment period: Day 15 to Day 28
- ✓ The same should apply thereafter, and the final period between the scheduled study visits should be Week 48 to Week 52 of the treatment period: Day 337 to the day before the day of blood sampling for hematology tests at Week 52 of the treatment period. However, for subjects who discontinued their treatment, the final period between the scheduled study visits should be up to the day before discontinuation.

\*2: If there are multiple applicable doses, the sum of the calculated values for each dose should be used.

\*3: The number of days without drug administration other than drug interruption should not be excluded from the “period of administration (days).”

\*4: 14 days up to Week 12 of the treatment period and 28 days after Week 12 of the treatment period. However, for subjects who discontinued their treatment, the final period between the scheduled study visits (days) should be the actual number of days until the day before discontinuation.

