\*5: “Period from the day of administration of darbepoetin alfa to the day of next administration of darbepoetin alfa.” However, the first treatment period (days) during the scheduled study visit period should be “period from the start date during the scheduled study visit period to the day before the day of the first darbepoetin alfa administration date after the start date during the scheduled study visit period” and the last treatment period (days) should be “from the last day of darbepoetin alfa administration during the scheduled study visit period to the day before the day of the last treatment or the day before discontinuation during the scheduled study visit period.”

The following formula should be used when no darbepoetin alfa is administered during the scheduled study visit period.

Mean weekly dose of darbepoetin alfa = Weekly dose of darbepoetin alfa immediately before the period between scheduled study visits

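### SAP section 4.10 does not separate a scheduled gap between darbepoetin injections from a drug interruption, so the descriptive mean weekly dose can be positive when none was given

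*SAP*

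**What the plan says.** The wording below is the same in section 4.10 of the final SAP and of the Phase 1 SAP.

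- **Carry-forward rule.** It begins "The following formula should be used when no darbepoetin alfa is administered during the scheduled study visit period" and gives "Mean weekly dose of darbepoetin alfa = Weekly dose of darbepoetin alfa immediately before the period between scheduled study visits". It sets no condition on why there was no injection.
- **Darbepoetin days (note *5).** The period credited to a dose is "Period from the day of administration of darbepoetin alfa to the day of next administration of darbepoetin alfa", with adjustments at the two ends of each visit interval. Interruption days are not taken out.
- **Tablet days (note *3, attached to the MT-6548 formula only).** "The number of days without drug administration other than drug interruption should not be excluded from the" period of administration. Missed days therefore stay in, and interruption days are the exception.
- **Denominator (note *4, both drugs).** "14 days up to Week 12 of the treatment period and 28 days after Week 12 of the treatment period", apart from a subject's last interval before discontinuation.

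Section 4.6 identifies an interruption of either drug by a CRF entry of zero: "First day of study drug interruption: The day of administration when" 0 mg or 0 µg is first recorded as the daily dose. Section 4.11 defines cumulative darbepoetin dosage from the doses actually given.

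Protocol 8.3.3 stops both drugs together: "If interruption of study drug administration is necessary, administration of MT-6548 Tablets and darbepoetin alfa injection should be discontinued". One trigger is "If Hb levels are >13.0 g/dL, study drug administration should be discontinued", with resumption once Hb has come down to 12.0 g/dL or lower and no limit on how long that may take. Protocol 12.3 and 12.4 add an interruption for raised ALT or AST.

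**The concern.** The carry-forward rule has a sound purpose. Protocol 8.3.3 allows dosing every 4 weeks, while visit intervals are 14 days up to Week 12, so some intervals contain no injection although the subject is on treatment. Recording zero there would be wrong.

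The same wording also catches an interval with no injection because dosing was stopped. Such intervals are foreseeable: the high-Hb interruption has no time limit, and section 4.6 of the final SAP provides for an interruption that runs to Week 52. On a plain reading, that interval takes the weekly dose from before the stop. Note *5 does the same within an interval, because the last injection before an interruption is credited until the next injection or the end of the interval.

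The protocol interrupts tablets and injections together, yet the derivation treats the event differently in the two arms. At stake is the accuracy of a listed endpoint, study drug dosage, as summarised by visit interval, over the whole treatment period, by baseline Hb category, by facility and by subgroup.

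**Working it through.** Neither SAP states a figure that rests on this rule, so there is none to reproduce. The check applies the 4.10 formulas to hypothetical subjects.

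**Inputs.** The formulas and interval lengths are those of 4.10. The illustrative doses are 300 mg/day (the protocol's starting tablet dose) and 60 µg (a step in the darbepoetin table). The interruption lengths and the share f are assumptions.

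**1. Whole 28-day interval interrupted.**
- Tablets: 300 × 0/28 = 0 mg/day. The zero is inferred: *3 removes interruption days from the numerator and *4 fixes the denominator.
- Darbepoetin 60 µg weekly: no injection in the interval, so 60 µg/week is carried forward. Amount given: 0.

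**2. Last 14 of 28 days interrupted, injections on days 1 and 8.**
- Tablets: 300 × 14/28 = 150 mg/day.
- Darbepoetin under *5: the two injections cover all 28 days, so (60/7) × 28/28 × 7 = 60 µg/week.
- With interruption days at zero: (60/7) × 14/28 × 7 = 30 µg/week.

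**3. Scheduled gap.** For 60 µg every 4 weeks and a 14-day interval with no injection, the weekly dose is 60/4 = 15 µg. Carrying 15 forward is right; entering 0 would be wrong.

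**4. Arm mean for one interval.** Let a share f be interrupted throughout, with every subject's prior weekly dose equal to d. The reported mean is d and the mean with interruptions at zero is (1−f)d. The relative overstatement is d/[(1−f)d] − 1 = f/(1−f).

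| Assumed f | Overstatement |
|---|---|
| 2% | 0.02/0.98 = 2.0% |
| 5% | 0.05/0.95 = 5.3% |
| 10% | 0.10/0.90 = 11.1% |

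**5. Agreement with section 4.11.** For 60 µg weekly over 52 weeks with one 4-week interruption, the cumulative dosage is 48 × 60 = 2880 µg. The mean weekly doses imply 52 × 60 = 3120 µg. The gap is 240/2880 = 8.3%.

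**6. Test of a simple repair.** Suppose 60 µg every 4 weeks is injected on day 1 and 0 µg is entered on day 15. Setting the dose to zero from that entry credits 15 µg/week × 2 weeks = 30 µg, although 60 µg was given. Crediting the injection for its full 28 days gives 15 × 4 = 60 µg.

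**The case against.** The strongest reply is that the SAP elsewhere treats 0 µg as a recorded dose level. Section 4.10 bases the dose on the physician's prescription. Section 4.6 ties the first zero entry to a day of administration. Section 8.6.1.5 gives darbepoetin a 0 µg weekly-dose category for adverse events. On that view, once 0 µg is in force, the dose carried into a later interval is 0, and a zero entry inside an interval ends the preceding dose period.

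This reading is possible, but 4.10 does not state it. It also leaves a gap. If the zero entry falls at the start of an interval, the weekly dose immediately before that interval is still the positive one, and it is carried forward unless the zero entry itself counts as an administration. Two programmers could reasonably produce different tables. So the wording does not prove that every interrupted interval would be given the last non-zero dose; it fails to exclude it, and plain reading points that way.

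Three further objections stand and limit the point:
- Cumulative dosage in 4.11 is unaffected, and the SAPs tabulate interruptions by reason and arm.
- Tablet and injection doses are in different units, and their time courses are drawn separately by arm. The one regression on dose is in the MT-6548 group with CRP as the predictor. The link to Hb is limited to descriptive dose tables by baseline Hb category.
- The share interrupted has no source in the documents. Interrupted subjects may also have been on lower doses than the rest, because Protocol 8.3.3 already steps the dose down above 11.5 g/dL. The overstatement would then be smaller than f/(1−f).

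**Conclusion.** The point holds as a minor defect of derivation. On its plain wording, section 4.10 of both SAPs credits the previous weekly darbepoetin dose to time when dosing was interrupted, while interrupted tablet time counts as zero. For one subject the error can be the whole prior dose (60 against 0 µg/week in the example). For the arm mean in one interval it is f/(1−f), or 2.0% to 11.1% for f from 2% to 10%. That range rests on an assumed f, on equal prior doses, and on a 0 µg entry not counting as an administration.

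The effect is confined to descriptive summaries of mean weekly dose, and to their disagreement with section 4.11 for interrupted subjects. A reader might infer that comparator exposure is overstated throughout, or that the comparison of the arms is biased. The documents do not support either: cumulative dosage uses doses given, no efficacy or safety test uses the mean weekly dose, and no formal between-arm comparison of dose is planned.

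**What to change.** Restrict the carry-forward rule; do not delete it. In section 4.10 of both SAPs, in note *5 and in the last rule, state that:

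1. the previous weekly dose is carried into an interval without an injection only when the gap arises from the dosing interval in force;
2. each injection is credited for its own scheduled interval of 7, 14 or 28 days;
3. any remaining interruption days, identified by the 0 µg entries defined in 4.6, count as 0 µg until dosing resumes.

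The second step must come before the third; otherwise a long-interval injection is under-credited, as step 6 of the working shows.

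The cost is a short addition to each SAP, for which the existing errata sheets offer a route, plus minor reprogramming and a rerun of the affected dose tables and figures. The CRF already holds the zero entries. The change concerns the derivation only and leaves dosing and clinical management untouched.

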## 4.11 Cumulative dosage

The cumulative dosage of the study drug is defined by the following formula.

Cumulative dosage of MT-6548 =  $150 \text{ mg} \times \text{Days of } 150 \text{ mg administration} + 300 \text{ mg} \times \text{Days of } 300 \text{ mg administration} + 450 \text{ mg} \times \text{Days of } 450 \text{ mg administration} + 600 \text{ mg} \times \text{Days of } 600 \text{ mg administration}$

Number of administration days of X mg\* = Day when dose was changed from X mg – First day of X mg administration (not excluding the number of days of no drug administration)

If there are multiple applicable periods, the sum of them should be used.

\*: X indicates each dose of MT-6548.

The cumulative dosage of darbepoetin alfa is the sum of individual doses of darbepoetin alfa  $\times$  the number of administrations of individual doses.

#### 4.12 Adverse drug reactions

In the MT-6548 group, adverse events for which a causal relationship to MT-6548 tablets is evaluated as “reasonably possible” are defined as adverse drug reactions associated with MT-6548 tablets, and in the darbepoetin group, adverse events for which a causal relationship to darbepoetin alfa injection is evaluated as “reasonably possible” are defined as adverse drug reactions associated with darbepoetin alfa injection.

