X weeks prior to the first day of the screening period.	Same day of week from X weeks prior to the first day of the screening period
MT-6548 Tablet 150 mg	Each film-coated tablet contains 150 mg vadadustat.
MT-6548 Tablet placebo	Film-coated tablets visually indistinguishable from MT-6548 Tablet 150 mg without containing vadadustat
MT-6548 Tablet	MT-6548 Tablet 150 mg and MT-6548 Tablet placebo
Darbepoetin alfa injection active comparator	Visually indistinguishable plastic syringes, each (0.5 mL) containing 5, 10, 20, 40, or 60 µg of darbepoetin alfa (recombinant)
Darbepoetin alfa injection placebo	Plastic syringes visually indistinguishable from darbepoetin alfa injection active comparator without containing darbepoetin alfa (recombinant)
Darbepoetin alfa injection	Darbepoetin alfa active comparator and darbepoetin alfa placebo

Protocol Summary

1. Study title

A phase III, double blind, confirmatory study of MT-6548 compared to darbepoetin alfa in hemodialysis subjects with anemia associated with chronic kidney disease in Japan

2. Purpose of the study

The study will verify non-inferiority of MT-6548 in patients with anemia associated with hemodialysis-dependent chronic kidney disease (HD-CKD) who are currently treated with an erythropoiesis-stimulating agent (ESA) using hemoglobin (Hb) levels as a measure and darbepoetin alfa (recombinant) as a control drug and evaluate safety of long-term administration of MT-6548.

3. Subjects

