5.2 Dosage and administration

The investigator/subinvestigator will administer both MT-6548 Tablets and darbepoetin alfa injection to subjects during the treatment period. Contents of the study drug are shown below; subjects, study institution staff members, and monitoring personnel will remain blinded to treatment until the final data has been fixed at the end of the study. The kit code of the study drug will be notified on the Web registration system every time the study drug is prescribed.

MT-6548 group: MT-6548 Tablet 150 mg and darbepoetin alfa injection placebo will be administered.

Darbepoetin group: MT-6548 Tablet placebo and darbepoetin alfa injection active comparator will be administered.

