5.3 Randomization methods

5.3.1 Blinding methods

Treatment period Phase 1 of the main study will be double-blind. Blinding for the main study will be performed by not informing those involved in conducting the study of which study drug is being administered and by using a placebo indistinguishable from the active comparator. The key code for data up to Week 24 of treatment period Phase 1 will be opened after data are fixed. However, even after that point, blinding of subjects, study center staff, and monitoring staff will be maintained until completion of the final data are fixed at the end of the study. Details of the procedure of maintaining the blindness will be separately defined before opening of the key code.

The organization contracted to perform randomization will create one original and one copy of the material list and one original each of the randomized key code list and allocation number list. To prevent disclosure of key code information to unauthorized parties, they will store and manage originals of the material list, randomized key code list, and allocation number list in a secure manner until the key code is opened. One original each of the material list, randomized key code list, and allocation number list will be opened when all CRFs for treatment period Phase 1 have been completed, data lock has occurred, and the manner of handling the data has been determined.

Upon receiving a request from the sponsor, the organization contracted to perform randomization will submit one copy of the material list to the sponsor's investigational drug QA manager for allocation of the study drugs. The sponsor's investigational drug manufacturing control manager will prepare study drugs with affixed kit codes based on the material list. They will prepare MT-6548 Tablet in such a way that the placebo and active comparator cannot be distinguished by their external appearance. They will also prepare darbepoetin alfa injection in such a way that the placebo and active comparator, as well as the different strengths, cannot be distinguished by their external appearance. To prevent disclosure of key code information to parties not involved in study drug allocation, the sponsor's investigational drug QA manager will store and manage the copy of the material list in a secure manner until the key code is opened.

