8.3 Dosage and administration

The investigator/subinvestigator will administer both MT-6548 Tablets and darbepoetin alfa injection to subjects during the treatment period. Contents of the study drug are shown below; subjects, study institution staff members, and monitoring personnel will remain blinded to treatment until the final data has been fixed at the end of the study. The kit code of the study drug will be notified on the Web registration system every time the study drug is prescribed.

MT-6548 group: MT-6548 Tablet 150 mg and darbepoetin alfa injection placebo will be administered.

Darbepoetin group: MT-6548 Tablet placebo and darbepoetin alfa injection active comparator will

be administered.

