The investigator/subinvestigator will assess whether or not there is a logical possibility that MT-6548 Tablet or darbepoetin alfa injection caused the AE. This assessment will take into account factors not related to the study drug, including risk factors such as natural course and concurrent treatments for underlying or concomitant diseases, as well as the temporal relationship between the study drugs and the event (recurrence after resuming administration, elimination after discontinuation, etc.). AEs for which a logical possibility of a causal relationship with MT-6548 Tablet exists will be treated as ADRs of MT-6548 Tablet, and AEs for which a logical possibility of a causal relationship with darbepoetin alfa injection

exists will be treated as ADRs of darbepoetin alfa injection.

- (a) Causal relationship with MT-6548 Tablet
 - 1. Logical possibility
 - 2. No logical possibility
- (b) Causal relationship with darbepoetin alfa injection
 - 1. Logical possibility
 - 2. No logical possibility

5) Outcome

AE outcomes are classified as follows:

- 1. Recovery
- 2. Relief
- 3. Not recovered
- 4. Recovered with sequelae
- 5. Death
- 6. Unknown

6) Date of outcome

Date of outcome is determined according to the following criteria:

Recovery: Date of recovery. If date of recovery is not known, use date on which recovery was confirmed or determined.

Relief: Date on which relief was confirmed or determined.

Not recovered: Date on which “not recovered” was confirmed or determined.

Recovered with sequelae: Date on which “recovered with sequelae” was confirmed or determined.

Death: Date of death. If date is not known, use date of confirmation or determination.

Unknown: Date of death if outcome is unknown due to death of subject for cause other than the relevant AE. For other circumstances use date of confirmation or determination.

7) Action taken with the study drug

Actions taken with MT-6548 Tablet and darbepoetin alfa injection fall into the 6 categories listed below.

(a) Actions taken to MT-6548 Tablet

1. Discontinuation of administration (study withdrawal)
2. Drug holiday
3. Dosage increase
4. Dosage reduction
5. No action
6. Not applicable (occurred after final administration of study drug)

(b) Actions taken to darbepoetin alfa injection

[figure not shown]
1. Discontinuation of administration (study withdrawal)
2. Drug holiday
3. Dosage increase
4. Dosage reduction
5. No action

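### Adverse drug reactions are counted for a different product in each arm, so the side-by-side ADR columns are not like for like

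*SAP*

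**What the plan says.** Protocol 8.3 sets out the double-dummy. In the MT-6548 group, "MT-6548 Tablet 150 mg and darbepoetin alfa injection placebo will be administered"; in the darbepoetin group, "MT-6548 Tablet placebo and darbepoetin alfa injection active comparator will be administered".

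Protocol 9.2.4.2 has the investigator assess "whether or not there is a logical possibility that MT-6548 Tablet or darbepoetin alfa injection caused the AE", with a separate causality field for each product. It then defines reactions by product: "AEs for which a logical possibility of a causal relationship with MT-6548 Tablet exists will be treated as ADRs of MT-6548 Tablet", with a matching clause for the injection. Neither clause mentions the arm. The protocol's Definitions of Terms give MT-6548 Tablet as "MT-6548 Tablet 150 mg and MT-6548 Tablet placebo", and the injection is likewise defined to include its placebo.

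The people making these judgements do not know the allocation. After the Phase 1 key opening, Protocol 5.3.1 says that "blinding of subjects, study center staff, and monitoring staff will be maintained until completion of the final data are fixed".

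Section 4.12 of both SAPs restricts the count by arm. "In the MT-6548 group, adverse events for which a causal relationship to MT-6548 tablets is evaluated as" reasonably possible are the ADRs of that arm; "in the darbepoetin group, adverse events for which a causal relationship to darbepoetin alfa injection is evaluated as" reasonably possible are the ADRs of the other. Both SAPs' own definitions of terms describe the tablet and the injection as containing active drug.

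Protocol 13.3.3 and SAP 8.6.1.1 and 8.6.1.2 call for ADRs and serious ADRs by treatment group. Section 10 of each SAP declares no change from the protocol.

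**The concern.** Causality judgements can be compared between arms only because a blinded investigator faces the same two questions about every event in both arms. The SAP rule keeps the answer to one question in one arm and the answer to the other question in the other arm. A reader of the ADR table will take the two columns as the same quantity. They are not, and they can differ when the two drugs produce exactly the same events.

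The attributions that are dropped, those to the placebo tablet and the placebo injection, measure background suspicion of each product. They are what a reader needs to interpret the active-product column. At stake is any statement that one drug has more or fewer adverse drug reactions than the other, overall, for serious reactions, or by SOC and PT. The same definition also feeds the tables by severity, onset, dose, cumulative dose, interruption and subgroup.

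**Working it through.** **Plan's own figure.** The plan states no ADR rate or ADR comparison to reproduce. Its one design figure is the probability above 95% for the primary criterion. With SD 1.73, margin 0.75 and 150 per arm, SE = 1.73 × √(2/150) = 0.1998 and 0.75/0.1998 − 1.96 = 1.794. That gives power 0.964 for non-inferiority; simulation of the joint criterion gives 0.963. The figure agrees and is not in question here. Only the 150 per arm is used below.

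**Inputs**
- Products per arm and dual causality judgement: Protocol 8.3 and 9.2.4.2.
- Blinding of investigators: Protocol 5.3.1.
- Counting rule: Section 4.12 of each SAP.
- 150 subjects per arm: SAP 2.4.
- Attribution rates: not in the documents. All values below are assumptions.

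**Step 1: what is collected and what is counted.** Let pT be the probability that a subject has at least one event attributed to the tablet, and pI the same for the injection. If the drugs have identical adverse event profiles and blinding holds, pT and pI are the same in both arms.

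| Attribution | MT-6548 arm | Darbepoetin arm |
|---|---|---|
| Tablet | pT, counted | pT, dropped (placebo tablet) |
| Injection | pI, dropped (placebo injection) | pI, counted |

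**Step 2: expected gap.** The SAP compares along the diagonal, so the gap is pT − pI. Comparison along a row gives pT − pT = 0 or pI − pI = 0. An either-product count has the same rate in both arms, somewhere between max(pT, pI) and pT + pI, so its gap is also 0.

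**Step 3: size under assumed rates**, no true drug difference, 150 per arm:

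| pT / pI | Expected ADR subjects, MT-6548 vs darbepoetin | Gap under SAP rule | Gap under a common rule |
|---|---|---|---|
| 5% / 5% | 7.5 vs 7.5 | 0 points | 0 |
| 8% / 5% | 12 vs 7.5 | +3 | 0 |
| 10% / 5% | 15 vs 7.5 | +5 | 0 |
| 15% / 5% | 22.5 vs 7.5 | +10 | 0 |
| 5% / 10% | 7.5 vs 15 | −5 | 0 |

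**Step 4: scale against sampling error.** At 10%/5% the standard error of the difference is √(0.10 × 0.90/150 + 0.05 × 0.95/150) = 0.030, or 3.0 points, so a 5-point artefact is about 1.7 standard errors. Exact binomial enumeration gives the chance that a nominal 95% (Wald) interval would exclude zero: 0.049 at 5%/5%, 0.183 at 8%/5%, 0.385 at 10%/5% or 5%/10%, and 0.848 at 15%/5%. With a common rule and 10% in both arms it is 0.052. The plan calculates no such interval for ADRs; these figures only show how the gap compares with noise.

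**The case against.** The strongest reply is that the count is deliberate and sound. The SAPs define the tablet and injection as active product, so a darbepoetin subject takes no MT-6548 tablets in SAP terms, and a placebo cannot cause a pharmacological reaction. Section 4.12 then describes reactions to the drug actually received. That stands for a drug-profile table. It does not make two such profiles comparable when they are set side by side by arm.

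Several stronger readings are tempting, and the documents do not support them.

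- *A planned safety inference is invalid.* ADR output is numbers and incidence only. No ADR test, p-value or between-arm interval appears, and all-cause adverse events, serious adverse events, discontinuations and deaths are tabulated without attribution.
- *The rule works against MT-6548.* One might infer that investigators suspect a new tablet more than a familiar class of injection. The documents give no attribution rates, and the reverse is equally possible.
- *The SAPs contradict the protocol.* The protocol's product definition is silent on arm, and its 13.3.3 does not say which attribution feeds the by-arm ADR table. The SAPs narrow the definition without recording it, which is less than a contradiction.
- *The definition should be replaced throughout.* That would put events blamed on a placebo injection into vadadustat dose categories, and the reverse, in SAP 8.6.1.5 to 8.6.1.7.
- *No output shows both attributions.* The contents pages list output tables and listings (Sections 12 and 14) that are not in the text available here, so this cannot be confirmed.

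**Conclusion.** The point holds in a limited form. The arm-specific ADR count is a fair description of each active drug, but the ADR and serious ADR columns by treatment group do not form a like-for-like comparison. With identical adverse event profiles and intact blinding, their expected difference is pT − pI, which is zero only if the two products are equally suspected. If the profiles do differ, the displayed gap mixes that true difference with the difference in suspicion.

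Size and direction are unknown. The range of −5 to +10 points shown above rests wholly on assumed rates. The consequence is confined to descriptive ADR statements between arms; the primary analysis and the all-cause safety comparisons are untouched. This is a cheap improvement to presentation.

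**What to change.** 1. For the overall and SOC/PT tables of ADRs and serious ADRs (SAP 8.6.1.1 and 8.6.1.2), show three counts in both arms: tablet-attributed, injection-attributed, and either product. Use these for any between-arm ADR statement.
2. Keep the Section 4.12 definition for the tables by dose before onset, cumulative dosage and interruption, and label those tables as active-product-only.
3. State the arm restriction in Section 10 of each SAP in place of the present declaration of no change.
4. The final-data SAP (8.5.4.3) reports the Phase 1 analysis as already done. Present the Phase 1 version as a labelled added analysis, with its reason, as Protocol 13.4 requires after data lock.

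The causality fields are already collected, so the cost is a few extra tables. The downsides are that some reactions will be shown against placebo products, and the either-product column will dilute a true product-specific difference, which is why the two single-product columns should stand beside it.
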